11.7.4. Other Safety Parameters

Physical examination data will be described. Where appropriate, changes from baseline will be presented by visit.

11.7.5. Interim Safety Review

An interim safety analysis is planned with the assistance of the DMC; the analysis will be a safety review when all patients have completed ≥ 12 weeks of treatment. If this review indicates potential safety concerns, the DMC may elect to have additional safety reviews for specific patients or all patients.

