Ataluren has been administered to patients with nonsense mutation cystic fibrosis (nmCF) as young as 6 years of age, patients with nmDMD as young as 5 years of age, and patients with nonsense mutation methylmalonic acidemia (nmMMA) as young as 3 years of age. No obvious differences have been apparent in the activity or safety profiles of ataluren in children relative to adults. Although patients <3 years of age have not been included in clinical studies, chronic toxicology studies in weanling rats and dogs support dosing of pediatric patients as young as 2 years of age. Refer to the Ataluren Investigator's Brochure (IB) for current information on use in pediatric patients.

This protocol describes a Phase 2, multiple-dose, open-label study evaluating the safety, pharmacokinetics (PK), and pharmacodynamics (PD) of ataluren in patients aged ≥ 2 to <5 years old with nmDMD. In nmDMD, early start of treatment is important and necessary and, therefore, it is relevant to understand the correct and tolerable dose in this age group, particularly since ataluren is dosed by weight. The study will include a 4-week screening period, a 4-week study period, and a 48-week extension period for patients who complete the 4-week study period (52 weeks total treatment). The objective of the extension period is to assess the long-term safety of chronic administration of ataluren in this patient population.

The primary objective of this study is to evaluate the safety of ataluren as measured by type, frequency, severity, timing, and relationship to study drug of treatment-emergent adverse events (TEAEs), laboratory abnormalities, and electrocardiograms (ECGs).

The secondary objectives are to determine the plasma PK of ataluren in patients aged ≥ 2 to < 5 years old with nmDMD, to monitor proximal muscle function using timed function tests (TFTs), to monitor physical function using the North Star Ambulatory Assessment (NSAA), to determine the effect of ataluren on weight, height, and body mass index (BMI), and to assess the palatability of ataluren.

This study provides ongoing safety review during open-label ataluren treatment. Furthermore, a planned interim safety analysis will be conducted by an independent data monitoring committee (DMC) when all patients have completed 12 weeks of treatment and additionally as needed.

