6.2.2. Duration of Treatment

The study duration will be 4 weeks during the PK portion and 48 weeks during the extension period (52 weeks total). Initial data assessment and reporting will be after all patients complete first 4 weeks (safety and PK) to satisfy Pediatric Investigation Plan (PIP) requirements and an additional report will be issued after completion of 48 weeks extension). The study may be terminated by the sponsor at any time and for any reason, eg, the clinical development of ataluren in dystrophinopathy is discontinued.

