8.2.1.2. Treatment Visits

During the treatment period, each patient will return to the clinical research facility during Week 0 (Visit 2) and Week 4 (Visit 3) for PK testing, and Week 16 (Visit 4), Week 28 (Visit 5), Week 40 (Visit 6), and Week 52 (Visit 7/ET).

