8.2.7.2. Biochemistry Laboratory Assessment

Biochemistry laboratory assessments will include sodium, potassium, chloride, bicarbonate, blood urea nitrogen, creatinine, magnesium, calcium, phosphorus, uric acid, glucose, total protein, albumin, bilirubin (total, direct, and indirect), AST, ALT, GGT, CK, lactate dehydrogenase, alkaline phosphatase, total cholesterol, high-density lipoprotein, low-density lipoprotein, triglycerides, and cystatin C. These parameters will be measured at every protocol-specified study visit. The study manual should be referenced for collection, processing, and shipping information.

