14.2.4. Safety Monitoring

In defining therapeutic activity in a particular clinical setting, it is imperative that the drug's safety profile be fully characterized. As is conventional in all clinical studies, proper description of each AE or laboratory abnormality requires an understanding of the type, incidence, timing, severity, and relatedness to study drug. In this study, particular focus will be placed on monitoring for renal adverse findings. For consistency of interpretation, AEs will be coded using the standard MedDRA, and the severity of these events will be graded using the well-defined CTCAE Version 4.0. Standard definitions for seriousness will be applied. Particular attention will be paid to any AEs causing discontinuation of ataluren and to SAEs requiring rapid regulatory reporting.

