3.8. Interim Analyses

An interim safety analysis is planned and will be conducted by an independent Data Monitoring Committee (DMC). The analysis will be based on a safety review when all subjects have completed at least 12 weeks of treatment. The safety analysis plan will be prepared separately.

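### Does the DMC's 12-week safety review need a named data-cut visit, given that no Week 12 visit exists?

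*Protocol*

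**What the plan says.** Three places set the timing of the only scheduled DMC review.

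- Protocol 11.7.5 (Interim Safety Review): "the analysis will be a safety review when all patients have completed ≥ 12 weeks of treatment".
- Protocol 1 (Overview): "when all patients have completed 12 weeks of treatment and additionally as needed".
- SAP 3.8 (Interim Analyses): "The analysis will be based on a safety review when all subjects have completed at least 12 weeks of treatment". The same section says that a safety analysis plan will be written as a separate document.

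Protocol 8.1 and 8.2.1.2 place the on-treatment visits at Weeks 0, 4, 16, 28, 40 and 52, with a window of two days either side. Of the biochemistry tests, which include creatinine and cystatin C, Protocol 8.2.7.2 says: "These parameters will be measured at every protocol-specified study visit". Hematology, urinalysis and vital signs follow the same visits.

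On further reviews, Protocol 1 allows them whenever needed. Protocol 11.7.5 adds: "If this review indicates potential safety concerns, the DMC may elect to have additional safety reviews for specific patients or all patients". Protocol 12 describes a DMC that acts independently of the sponsor, advises on risk and benefit as the study proceeds, and has a charter. Protocol 6.2.2 separately plans a safety and PK assessment once every patient has completed 4 weeks, without describing it as a DMC review.

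**The concern.** The review is set at a time when nothing is measured. A literal reader could freeze the data on Day 84, and the boys enrolled last would then contribute only their baseline and Week 4 results. That matters most for renal safety, of which Protocol 14.2.4 says: "In this study, particular focus will be placed on monitoring for renal adverse findings". Protocol 6.3.2 distinguishes transient creatinine rises from those sustained beyond 4 weeks, and one scheduled post-baseline value cannot separate the two.

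Two further features add to the doubt. The trigger waits for the last patient, so slow enrollment postpones the only scheduled DMC look. And 11.7.5, read alone, seems to provide for extra reviews only after the planned one has raised a concern, whereas Section 1 sets no such condition. At stake would be a single planned look that rests on old laboratory data for some boys, with no clear route to another.

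**Working it through.** **Schedule arithmetic.** Inputs are the visit days in Protocol Table 2 and SAP 3.3.

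- Trigger: 12 × 7 = Day 84.
- Nearest visits: Day 28 (window 26–30) and Day 112 (window 110–114). Neither window contains Day 84.
- Age of the last scheduled results on Day 84: 84 − 28 = 56 days. Wait to the next visit: 112 − 84 = 28 days.
- Visit spacing from Week 4 to Week 52 is 84 days throughout. Week 16 is therefore the first scheduled visit that satisfies the 12-week minimum.

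**How many boys a Day 84 cut would affect.** Accrual time is not stated. Assume exactly 12 boys (the protocol says at least 12) with evenly spaced starts over *A* weeks. Boy *i* (*i* = 0 to 11) enters at *iA*/11. When the last boy reaches *c* weeks, the study is at week *A* + *c*, and boy *i* has received min(52, *A* + *c* − *iA*/11) weeks of treatment.

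With *c* = 12, a boy has not reached Week 16 if *A*(11 − *i*)/11 < 4. For *A* = 26 this requires 11 − *i* < 1.69, which gives 2 boys.

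**What a Week 16 cut costs.** The share of planned exposure already given is the sum of the individual exposures divided by 12 × 52 = 624 patient-weeks. For *A* = 26 the mean exposure is 12 + 13 = 25 weeks at *c* = 12, so 25/52 = 48%. At *c* = 16 it is 29/52 = 56%.

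| Accrual *A* (weeks) | Boys with nothing scheduled after Week 4 (*c* = 12) | Exposure given, *c* = 12 | Exposure given, *c* = 16 |
|---|---|---|---|
| 0 | 12 | 23% | 31% |
| 12 | 4 | 35% | 42% |
| 26 | 2 | 48% | 56% |
| 40 | 2 | 62% | 69% |
| 52 | 1 | 70% | 75% |

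Moving the cut to Week 16 thus updates the laboratory data of a few boys (all of them only if they start together) and delays the full-cohort review by four weeks. It adds no ECG, because none is scheduled between Weeks 4 and 52 (Protocol 8.2.8).

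**An earlier look.** A DMC summary when the first six boys complete Week 4 would fall at study week 5*A*/11 + 4. For *A* = 26 that is week 15.8, against 26 + 12 = 38 for the 12-week trigger: 22 weeks sooner, with 10% of exposure given. It would need its own data cut and one more DMC meeting.

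**The timing statements side by side.** Protocol 11.7.5 and SAP 3.8 set a floor. Section 1 omits the words that mark it as one, yet a patient seen at Week 16 has also completed 12 weeks, so a Week 16 cut satisfies all three. None of them says which data are frozen, or when.

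**The extra-review statements side by side.** Section 1 is general. Section 11.7.5 covers one particular case, follow-up of a concern found at the planned review, and adds that it may be limited to specific patients. It is permissive and rules nothing out, so both can be followed at once.

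**The case for a change.** The strongest case for a change is that the review is the only scheduled independent look in a very young population. Protocol 1 says that patients under 3 years had not been included in clinical studies, and Protocol 14.1.2 describes three patients under 6, treated for 28 days at this dose. A few words would name the cut and align Section 1 with 11.7.5. The charter and the separate safety plan were not available, so nobody reading only the protocol and SAP can be sure that they settle the point. Slow accrual also has real consequences: at 40 weeks or more the first boy has finished treatment before the trigger is reached (40 + 12 = 52).

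The facts in this stand: there is no Week 12 visit, no cut is named in the protocol or SAP, and the extra-review wording is uneven. The inference does not. Old laboratory data arise only from a Day 84 freeze that no passage specifies. The accrual argument is really one for an additional early look. That is a reasonable preference, but no inconsistency in the plan calls for it, and neither the number six nor Week 4 comes from the documents. Meanwhile the DMC can meet as needed, dose interruptions go to the medical monitor (Protocol 6.3.2), further tests can be done when clinically indicated (Protocol 8.2.14), and serious events are reported within 24 hours (Protocol 9.8).

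**Conclusion.** No change follows. The unnamed data cut is a gap that the people preparing the DMC package will fill sensibly: the text permits Week 16, it is the first visit that meets the minimum, and the separate safety plan is the expected place to record it. Choosing between a cut near 12 weeks and one at Week 16 is a fair trade-off between fresher results and an earlier review, worth about 8 percentage points of planned exposure at 26 weeks' accrual. The extra-review wording is uneven drafting with no practical effect. Neither document attaches a hypothesis test or stopping boundary to the review, and the main summaries are descriptive, so no reported result would change.

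This rests on two assumptions. One is that the charter or safety plan does not impose a Day 84 freeze. If it did, 4 or fewer of 12 boys would lack scheduled results after Week 4 once accrual takes 12 weeks or longer, and all 12 would if they started together. The other is evenly spaced enrollment of exactly 12 boys, which the documents do not state; clustered late enrollment would raise the count.

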11.8. Treatment Administration and Drug Compliance

Study drug compliance will be assessed by unused study drug reporting. Compliance will be analyzed as a percentage of drug actually taken relative to the amount that was specified to be taken during the study.

11.9. Use of Concomitant Medication and Supportive Therapy

Concomitant medications will be coded by means of the World Health Organization Drug Dictionary (WHODRUG) into Anatomical-Therapeutic-Chemical (ATC) classification codes. The type and timing of use of specific concomitant medications will be listed and summarized. The frequency, timing, type, and amount of any other therapies for dystrophinopathy will be considered with special interest.

11.10. Palatability Questionnaire

Palatability data will be summarized descriptively.

11.11. Exploration of Correlations

Correlations between patient characteristics and outcome measures, and correlations among outcomes measures may be explored using regression models or other appropriate techniques.

12. STUDY COMMITTEES

A DMC, operating autonomously from the sponsor and the clinical investigators, will be responsible for providing independent recommendations to PTC Therapeutics about evolving risk-benefit observed in the course of the study and any modifications required during the course of the study. The DMC will comprise appropriately qualified personnel as detailed in the DMC charter. The DMC will be chaired by one of those individuals. DMC members must not be actively involved in study design, conduct, or daily management of this study and must not have financial, proprietary, professional, or other interests that may affect impartial, independent decision-making. Specialists may be invited to participate as non-voting members at any time if additional expertise is desired.

13. OBLIGATIONS OF THE INVESTIGATOR AND THE SPONSOR

13.1. Compliance with Ethical and Regulatory Guidelines

The Investigator is responsible for ensuring that the clinical study is performed in accordance with the International Council on Harmonisation (ICH) GCP guidance documents and the Declaration of Helsinki.

13.2. Institutional Review Board/Independent Ethics Committee

Prior to enrollment of patients into the study, as required by regulatory authorities, the protocol and informed consent document will be reviewed and approved by an appropriate IRB/IEC. By signing the protocol, the Investigator assures that approval of the protocol will be obtained from the IRB/IEC and that all aspects of the IRB/IEC review will be conducted in accordance with current regulations. Amendments to the protocol will be subject to the same IRB/IEC review requirements as the original protocol. Only changes necessary to eliminate apparent immediate hazards to the patients may be initiated prior to IRB/IEC approval. In that event, the Investigator must notify the IRB/IEC and PTC Therapeutics in writing within 5 working days after implementation. The Investigator will also promptly notify the IRB/IEC of any serious, unexpected AEs or any other information that may affect the safe use of the drug during the course of the study.

A letter documenting the IRB/IEC approval and a list of the names and titles of the IRB/IEC members must be received by PTC Therapeutics prior to the initiation of the study. All correspondence with the IRB/IEC should be retained in the Investigator's study file.

The Investigator shall submit a progress report, at least once yearly, to the IRB/IEC, and must provide a copy to PTC Therapeutics. As soon as possible after completion or termination of the study, the Investigator will submit a final report to the IRB/IEC and to PTC Therapeutics. This report should include the dates of initiation and completion of the study, a description of any changes in study procedures or amendments to the protocol, any deviations from the protocol, the number and type of patients evaluated, the number of patients who discontinued (and the reasons for discontinuation), the number of patients who completed the study, and the results of the study, including a description of any AEs. PTC Therapeutics will assist the Investigator in the preparation of this report, as needed.

13.3. Informed Consent/Assent

By signing the protocol, the Investigator assures that informed consent/assent will be obtained from each patient and/or parent/legal guardian prior to study entry and that the informed consent/assent will be obtained in accordance with current regulations.

The Investigator or sub-investigator will give each patient and/or parent/guardian full and adequate verbal and written information regarding the objectives and procedures of the study and the possible risks involved. An informed consent/assent document will be provided to each patient and/or parent/guardian in a language in which the patient or parent/guardian is fluent. This information must be provided to the patient or parent/guardian prior to undertaking any study-related procedure. Adequate time should be provided for the patient and/or

parent/guardian to read the informed consent, to understand the risks and benefits of participating in the study, and to ask any questions that the patient and/or parent/guardian may have about the study. The patient and/or parent/guardian should be able to ask additional questions as and when needed during the conduct of the study. The patient's and/or parent(s)/guardian signature (as required by local regulations) on the informed consent form should be obtained at the investigational site in the presence of the Investigator or a qualified representative (eg, sub-investigator). Where applicable, the patient will sign an age-appropriate assent form.

Each patient or parent/guardian will be given a copy of the signed consent/assent form. The original signed informed consent forms will be retained by the Investigator with the study records.

The written patient information must not be changed without prior approval by PTC Therapeutics and the IRB/IEC.

13.4. Case Report Forms

An eCRF is required and must be completed for each patient, with all required study data accurately recorded such that the information matches the data contained in medical records (eg, physicians' notes, nurses' notes, clinic charts, and other study-specific source documents). The eCRFs exist within a Web-based EDC system managed by the data management CRO for this study. After the Investigator or the Investigator's designees (eg, research coordinators) have been appropriately trained, they will be given access to the EDC system and will enter the data required by the protocol into the EDC system. Any change of data will be made via the EDC system, with all changes tracked by the system to provide an audit trail.

With an electronic signature, the Investigator certifies that the data are complete and accurate prior to database lock. This electronic signature serves to attest that the information contained in the eCRFs is true. After database lock, the investigational site will receive a CD-ROM and/or paper copies of the patient data for archiving at the investigational site. At all times, the principal Investigator has final responsibility for the accuracy and authenticity of all clinical data entered onto the eCRFs and/or reported to PTC Therapeutics from the investigational site.

13.5. Study Records

During the study, the Investigator will maintain adequate records for the study, including medical records, source document records detailing the progress of the study for each patient, laboratory reports, a CD-ROM or paper copy of the data that have been captured in the EDC for each patient (electronic equivalents of CRFs), paper CRFs, signed informed consent forms, ataluren reconciliation and dispensing records, correspondence with the IRB/IEC, AE reports, and information regarding patient discontinuation and completion of the study. Current regulations require PTC Therapeutics (or an authorized designee) to inspect all documents and records required to be maintained by the Investigator, including but not limited to medical records (office, clinic, or hospital) for the patients enrolled in this study. These regulations also allow the same records to be inspected by authorized representatives of the FDA, Health Canada, or other regulatory authorities.

13.6. Confidentiality

Research records will be collected and stored in a manner that protects the confidentiality of patient information. The names and identities of all research patients will be kept in strict confidence and will not appear on eCRFs, paper CRFs, or other records provided to or retained by PTC Therapeutics (or its authorized designee). The names and identities of the patients need not be divulged; however, the records must nevertheless be inspected. This will be accomplished by redacting the patient's name and replacing the name with the patient's study identification number on any record provided to or retained by PTC Therapeutics. The informed consent form must include appropriate statements explaining these requirements.

By signing this protocol, the Investigator affirms to PTC Therapeutics that the Investigator will maintain, in confidence, information furnished by PTC Therapeutics and will divulge such information to the IRB/IEC under an appropriate understanding of confidentiality with such board.

13.7. Retention of Records

To enable evaluations and/or audits from regulatory authorities or PTC Therapeutics, the Investigator agrees to keep accurate and complete records, including the identity of all participating patients (sufficient information to link eCRFs and clinic records), all original signed informed consent forms, CD-ROM or paper copies of the data that have been captured in the EDC for each patient (electronic equivalents of CRFs), and detailed records of ataluren disposition. All records and documents pertaining to the study (including but not limited to those outlined in Section 13.5 above) will be maintained by the Investigator until notification is received from PTC Therapeutics that the records no longer need to be retained.

The Investigator must obtain written permission from PTC Therapeutics before disposing of any records. In order to avoid any possible errors, the Investigator will contact PTC Therapeutics prior to the destruction of any study records. The Investigator will promptly notify PTC Therapeutics in the event of accidental loss or destruction of any study records. If the Investigator relocates, retires, or for any reason withdraws from the study, the study records may be transferred to an acceptable designee, such as another Investigator, another institution, or to PTC Therapeutics.

13.8. Monitoring and Auditing

In accordance with 21 CFR Part 312.56 and/or relevant ICH guidelines, PTC Therapeutics or a designee will periodically inspect all eCRFs (see Section 13.4), study documents, research facilities, and clinical laboratory facilities associated with this study at mutually convenient times, before, during, and after completion of the study. As required by applicable regulations (Responsibilities of Sponsors and Investigators), the monitoring visits provide PTC Therapeutics with the opportunity to evaluate the progress of the study; verify the accuracy and completeness of data in the eCRFs; ensure that all protocol requirements, other relevant regulations, and Investigator's obligations are being fulfilled; and resolve any inconsistencies in the study records. This includes inspection of all documents and records required to be maintained by the Investigator, including but not limited to medical records (office, clinic, or hospital) for the patients in this study. The names and identities of all research subjects will be kept in strict

confidence and will not appear on eCRFs or other records provided to or retained by PTC Therapeutics. The Investigator/institution guarantees direct access to source documents by PTC Therapeutics and appropriate regulatory authorities.

The investigational site may also be subject to review by the IRB/IEC, to quality assurance audits performed by PTC Therapeutics or a designee, and/or to inspection by regulatory authorities. The GCP regulations also require the Investigator to allow authorized representatives of the regulatory authorities to inspect and make copies of the same records.

It is important that the Investigator and relevant institutional personnel are available during the monitoring visits and possible audits or inspections, and that sufficient time is devoted to the process.

